16.3 Population for Analysis

The following populations will be considered for the analysis:

- The modified intention to treat (mITT) population is defined as all included patients with at least a single dose of study drug.
- The per-protocol population (PP) will include patients in the mITT population who sufficiently comply with the protocol. Criteria for inclusion in the PP population will be defined prior to database lock.

- The safety population will include all patients with at least a single dose of study drug, identical to the mITT population.

16.4 Planned analyses

The main statistical analysis is planned when

- The planned number of patients have been included
- All included patients have either finalised their last assessment of the primary endpoint or has/is withdrawn according to protocol procedures
- All data have been entered, verified and validated.

Further analyses will be performed subsequently to the main analyses as more efficacy data are available (such as disease progression and death).

16.5 Statistical analyses

The primary parameter to be estimated is the proportion of patients with a negative PET-CT with 95% confidence limits by the Wilson method. The primary analysis will be performed on the mITT population.

Dichotomous endpoints will be handled as the primary parameter in addition to mixed model logistic regression for repeated measurements. Time to event endpoints will be presented using Kaplan-Meier plots, while repeated continuous endpoints will be analysed using linear mixed models. All parameters will be analysed both in the mITT and PP populations.

Unless otherwise specified, all estimates will be presented with 95% confidence limits. Parameter estimates might be compared to historical estimates, pre-specified prior to any analyses.

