| 
Study Endpoints
 
Primary:
 
 - Proportion of PET-CT positivity after standard first line therapy - Change from PET-CT positivity to PET-CT negativity after 4 cycles of KRd consolidation. 
Secondary:
 
 - MRD negativity by 8-colour EuroFlow after 4 cycles of KRD consolidation. - Safety - Overall response rate - Progression-free survival (PFS) - Time to next treatment (TTNT) - Overall survival (OS) - Quality of life during and after KRD consolidation |
| 
Treatment schedule
 
Four cycles of Carfilzomib-Lenalidomide-Dexamethason
 
The carfilzomib dose is 20-20-36-36-36-36 mg/m² on day 1, 2, 8, 9, 15 and 16 in the first cycle. It will be increased to 36 mg/m² on days 1, 2, 8, 9, 15 and 16 in cycles 2-4.
 
The oral dexamethasone dose is 40 mg weekly throughout the study for patients under 75 years of age. 20 mg for patients over 75 years of age.
 
The Revlimid dose is 25 mg on days 1-21 in every cycle.
 |

Inclusion criteria (selected)

1. Prior confirmed diagnosis of multiple myeloma (2014).
2. Received standard first line treatment with at least partial response. Standard first line treatment is defined as VRD, VTD or VCD followed by ASCT, with or without lenalidomide maintenance
3. Carfilzomib naïve
4. Eastern Cooperative Oncology Group (ECOG) performance status 0-2.
5. Absolute neutrophil count (ANC) $\geq 0,5 \times 10^9/L$ and platelet count $>35 \times 10^9/L$.
6. At least very good partial remission (VGPR) from first line treatment

Exclusion criteria (selected)

1. Change of first line treatment because of stable or progressive disease.
2. Major surgery within 28 days before enrollment.
3. Radiotherapy within 14 days before enrollment.
4. Glucocorticoid therapy within the 14 days prior to inclusion that exceeds a cumulative dose of 160 mg dexamethasone or 1000 mg prednisone.
5. Patients who started treatment more than 12 month before screening
6. Central nervous system involvement.
7. Uncontrolled heart disease, including congestive heart failure (NYHA III-IV), uncontrolled angina pectoris, uncontrolled conduction abnormalities, acute diffuse infiltrative pulmonary disease, pericardial disease or myocardial infarction within 6 months prior to enrollment
8. Uncontrolled hypertension or uncontrolled diabetes despite medication
9. Active hepatitis B or C infection or known human immunodeficiency virus (HIV) positivity.

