7. INVESTIGATIONAL PLAN – STUDY DESIGN

This is an investigator initiated, academic, non-randomized, open-label multicenter study for consolidation in patients with multiple myeloma after standard first line treatment.

CONPET vs 14, 24th October 2018

After a standard induction regime with ASCT, patients can be included in the study. A PET-CT will be performed, patients with a negative PET result will go out of the study, with a strong recommendation of standard-of-care treatment, as specified below. Patients with a positive PET result will receive four cycles of KRd followed by standard-of-care treatment with lenalidomide maintenance 10-15mg once daily

A new PET-CT-evaluation will be performed after completed consolidation. At inclusion in the study, MRD samples will be taken from all patients. We will repeat these samples after completed consolidation. The goals of the study are to evaluate what proportion of patients are PET-positive after standard first line treatment and how many of these can become PET-negative after KRd consolidation. The study will explore the dynamics of MRD status in this setting, and the correspondence between these two methods. Review of PET-CTs will be central and blinded.

The PET-CT-negative group will have long time follow up through their local doctor for PFS and OS

The study is a phase 2 study, with 50 PET-positive patients, to show the feasibility, safety and efficacy of this design.

Inclusion of patients will continue until 50 PET-positive patients have been included.

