8. STUDY POPULATION

8.1 Inclusion criteria

Each patient must meet all the following inclusion criteria to be enrolled in the study:

1. At least 18 years of age, with at least 6 months expected survival.
2. Prior confirmed diagnosis of multiple myeloma (2014) (16).
3. Received standard first line treatment with at least a very good partial response (VGPR), according to IMWGs criteria . Standard first line treatment is defined as

VRD, VTD or VCD followed by ASCT with or without lenalidomide maintenance initiated (Patients where the monoclonal component or dFLC increases during the period from best response to screening can be included if there is no progressive disease.)

4. Patients must be carfilzomib naïve.
5. A positive PET-CT result from central reviewer in the screening period

6. Successful FISH evaluation performed with available results
7. Voluntary written consent must be given before performance of any study related procedure not part of standard medical care, with the understanding that the patient may withdraw consent at any time without prejudice to future medical care.
8. Females of childbearing potential (FCBPs) must have a confirmed negative serum pregnancy test within the 7 days prior to inclusion
9. FCBPs and male subjects who are sexually active with FCBP must agree to use highly effective concomitant methods of contraceptive during the study and for 30 days following the last study drug dose. Male subjects must use contraception and refrain from donating sperm for at least 90 days after the last dose of carfilzomib.
10. Eastern Cooperative Oncology Group (ECOG) performance status 0-2. In patients >75 years of age, performance status 0-1.
11. Patients must meet the following adequate organ and bone marrow function within 21 days prior to inclusion:
 - Absolute neutrophil count (ANC) $\geq 0,5 \times 10^9/L$ and platelet count $35 \times 10^9/L$. Platelet transfusions to help patients meet eligibility criteria are not allowed within 3 days before study enrollment. Granulocyte growth factors are allowed to meet the inclusion criteria.
12. Patient must be willing and able to adhere to the study schedule and other protocol requirements.

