16.2 Endpoint definitions

Primary endpoint:

- Change from PET-CT positivity to PET-CT negativity at visit D Proportion of PET-CT positivity after standard first line therapy

Secondary endpoints are

- Change from MRD positivity to MRD negativity at visit D, as assessed by 8-colour Euroflow multiparameter flow cytometry
- Overall response after each treatment cycle.
- Progression-free survival (PFS) as defined as time from treatment initiation to progression defined using IMWG criteria for progressive disease.
- Time to next treatment (TTNT) as defined as time from treatment initiation (start of cycle 1) to start of cycle 1 in next cancer treatment cycle.
- Overall survival (OS) as defined as time from treatment initiation (start of cycle 1) to time of death
- Quality-of-Life (section 15.3 and study flow chart)

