16.7 Missing data

For dichotomous endpoints, missing data will be handled using worst case imputation. No imputation will be performed for time-to-event data, and incomplete registrations of event will be censored at last time of contact. Continuous endpoints will be analysed using mixed modes giving unbiased estimates under the assumption of missing at random.

Robustness analyses including complete case analyses, last observation carried forward, best case imputation and multiple imputation techniques might be considered if the rate of missing data is substantial.

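### PET-CT positivity after first-line therapy is a primary endpoint, but every analysis set in section 16.3 contains only dosed, PET-positive patients, so the estimate as written is 100% by construction

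*Protocol*

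**What the plan says.** The synopsis and section 16.2 both list two primary endpoints. One is "Proportion of PET-CT positivity after standard first line therapy". The other, in the synopsis wording, is "Change from PET-CT positivity to PET-CT negativity after 4 cycles of KRd consolidation". Section 6.1 puts both into the primary objective.

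Section 16.3 defines three populations. For the first: "The modified intention to treat (mITT) population is defined as all included patients with at least a single dose of study drug". The per-protocol set is drawn from the mITT, and the safety set is stated to be identical to it.

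Section 16.5 names one primary parameter, the proportion with a negative PET-CT, with Wilson 95% limits, and continues: "The primary analysis will be performed on the mITT population". It then says that dichotomous endpoints are handled in the same way as the primary parameter, and it assigns all parameters to both the mITT and per-protocol populations.

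On who is dosed, inclusion criterion 5 in section 8.1 requires "A positive PET-CT result from central reviewer in the screening period". Section 7 says that "patients with a negative PET result will go out of the study", while those with a positive result receive KRd.

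**The concern.** The proportion positive after first-line therapy needs everyone who was scanned in its denominator, negatives included. The populations in 16.3 hold only patients who received study drug, and study drug goes only to patients whose scan was positive. On any of these sets the numerator equals the denominator.

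This is a stated rule that gives an uninformative answer, not a detail left for later. A statistical analysis plan that followed 16.3 and 16.5 would report 100%. One that used the scanned patients would depart from the protocol for a primary endpoint. Leaving the denominator undefined also leaves room to choose, after results are known, between consented, otherwise eligible and scanned patients.

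**Working it through.** **Inputs**

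- Target of 50 PET-positive patients, with 50% positivity anticipated and therefore 100 scanned (section 16.1).
- Positivity of 30 to 40% in the outside data cited in section 4. The protocol calls that data set incomplete and expects a marginally higher rate after VTD or VCD plus transplant.
- Wilson 95% limits (section 16.5), with p = x/n and z = 1.96: [p + z²/(2n) ± z·√(p(1−p)/n + z²/(4n²))] / (1 + z²/n).

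**Step 1: reproduce the plan's own figures.** The screening number is 50/0.5 = 100, as stated. With n = 50, the Wilson formula returns all nine rows of the 16.1 table to three decimals, for example 0.366 to 0.634 at 0.5 and 0.043 to 0.214 at 0.1. With n = 100, the row for 0.5 would be 0.404 to 0.596, which is not what the table shows. The table therefore gives the precision of conversion among 50 treated patients. It does not give the precision of positivity among about 100 scanned.

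**Step 2: positivity on the defined sets.**

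- mITT requires dosing.
- Dosing requires inclusion, and criterion 5 makes a positive central scan a condition of inclusion.
- Patients with a negative scan leave before KRd.
- Per-protocol is a subset of the mITT, and safety equals it.

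So x = n in every set. When x = n, the lower Wilson limit reduces to n/(n + z²). For n = 50 it is 50/53.84 = 0.929, with an upper limit of 1.000. If only 48 were dosed, it would be 48/51.84 = 0.926. The point estimate is 100% in either case and does not depend on the true rate.

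**Step 3: positivity on the scanned patients.** Recruitment runs until there are 50 positives, so the number scanned is about 50 divided by the positivity rate, rounded up. At 50% this is 100. The Wilson centre is (0.5 + 0.0192)/1.0384 = 0.500 and the half-width is 1.96 × √(0.0025 + 0.000096)/1.0384 = 0.096.

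| Positivity rate | Scanned | Estimate | Wilson 95% interval |
|---|---|---|---|
| 50% (section 16.1) | 100 | 50/100 = 50% | 0.404 to 0.596 |
| 40% (section 4) | 125 | 50/125 = 40% | 0.318 to 0.488 |
| 30% (section 4) | 167 | 50/167 = 30% | 0.235 to 0.373 |

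Because recruitment stops at the fiftieth positive, the number scanned is itself random. The intervals treat it as fixed and are approximate in that respect.

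**Step 4: does a looser meaning of inclusion help?** Section 7 speaks of patients being included and then scanned, which conflicts with criterion 5. Even if inclusion in the mITT definition is read in the section 7 sense, the dosing requirement still removes every PET-negative patient.

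**The case against.** The sentence that puts the primary analysis on the mITT comes directly after the definition of the primary parameter as the proportion with a negative PET-CT. For that parameter, conversion, the mITT is a suitable set. A reader might infer that this sentence by itself moves positivity onto the mITT, but the text does not say so. This part of the objection stands. It does not rescue the positivity endpoint, because 16.5 then handles dichotomous endpoints like the primary parameter and sends all parameters to the mITT and per-protocol sets, and 16.3 offers no other set.

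A reader might also infer that half of the primary objective cannot be answered. The protocol does not support that. Section 7 has patients scanned at entry with central, blinded review. Sections 7 and 10 keep PET-negative patients under follow-up for progression-free and overall survival. Section 16.1 ties the positivity rate to about 100 scanned patients. The right denominator can be recovered, the endpoint is descriptive, and an analyst would notice a reported 100%.

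A third tempting reading concerns section 16.7: "For dichotomous endpoints, missing data will be handled using worst case imputation". One might infer that missing screening scans would be counted as positive and inflate the rate. The protocol does not say what worst case means for a prevalence. In the mITT as defined, the question cannot arise, because each eligible patient has a centrally read positive screening scan. The documents also give no rate of missing screening scans. No bias can be claimed on this ground.

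Finally, an analysis plan that is not shown could add a screened set. It would still contradict the sentence in 16.5 that covers all parameters, so the protocol text needs correcting.

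**Conclusion.** The point holds in this form: a declared primary endpoint is assigned to populations in which it can only equal 100%. As written the result is 50/50 (0.929 to 1.000). On the scanned patients it would be 50/100 (0.404 to 0.596) under the protocol's planning rate, or 40% (0.318 to 0.488) and 30% (0.235 to 0.373) at the rates cited in section 4. The 100% assumes no eligibility deviation, that is, no PET-negative patient dosed in error. The alternatives assume exactly 50 positives and treat the number scanned as fixed.

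The text is wrong and should be corrected, but the defect lies in the definition of sets and one over-broad sentence. It does not concern data collection, the use of the mITT for conversion, or the direction of imputation.

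**What to change.** - **Section 16.3:** add a PET-evaluated set, made up of all consented patients who meet the other eligibility criteria and have a centrally read screening PET-CT.
- **Section 16.5:** state that positivity is estimated on this set with a Wilson interval from observed scans, and that conversion is estimated on the mITT. Limit the sentence assigning all parameters to the mITT and per-protocol sets to post-treatment endpoints.
- **Section 16.1:** add the precision for about 100 scanned patients (0.404 to 0.596 at 50%), and label the existing table as n = 50.
- **Section 16.7:** state that, for the primary endpoints, the imputation rule applies to the post-KRd scan.
- **Sections 7 and 8.1:** reconcile the use of inclusion, which comes before the PET-CT in section 7 but depends on a positive PET-CT in criterion 5.

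The cost is a handful of sentences. No new procedure or patient is needed, since the screening scans and their central review are already planned.

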16.6 Safety analyses

Safety analyses will be performed in the safety population. Safety analyses will be descriptive and presented as summary tables.

16.7 Missing data

For dichotomous endpoints, missing data will be handled using worst case imputation. No imputation will be performed for time-to-event data, and incomplete registrations of event will be censored at last time of contact. Continuous endpoints will be analysed using mixed modes giving unbiased estimates under the assumption of missing at random.

Robustness analyses including complete case analyses, last observation carried forward, best case imputation and multiple imputation techniques might be considered if the rate of missing data is substantial.

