10. END OF STUDY

Inclusion in the study ends when 50 patients have had positive initial PET-CT results. After progressive disease, patients will be followed by telephone for overall survival. Patients with negative PET-CT results will be followed by telephone/fax for progressive-free survival and overall survival every second month (± 7 days).

The study will end with last patients last visit. There will be a post-study follow-up for overall survival in all patients, both with initial PET-CT positivity and negativity.

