13.5 Immunochemistry

Serum protein electrophoresis and immunofixation (IFE) at study entry, start of every cycle and every two months until progression. 24-h urine electrophoresis and immunofixation at study entry, the start of every cycle and every two months until progression. Serum free light chains (S-FLC) at study entry, start of every cycle and at every two months until progression

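### Section 16.7 as worded allows an event that is known but incompletely dated to be censored, which would bias the secondary OS, PFS and TTNT curves upward

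*Protocol*

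**What the plan says.** Protocol section 16.7 gives one rule for time-to-event endpoints: "No imputation will be performed for time-to-event data, and incomplete registrations of event will be censored at last time of contact". For binary endpoints the same section takes the opposite approach: "For dichotomous endpoints, missing data will be handled using worst case imputation".

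Section 16.2 defines the three endpoints concerned, all secondary, by their events:

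- For PFS it says: "Progression-free survival (PFS) as defined as time from treatment initiation to progression defined using IMWG criteria for progressive disease".
- TTNT is counted from the first day of KRd until the patient begins another anticancer regimen.
- For OS it says: "Overall survival (OS) as defined as time from treatment initiation (start of cycle 1) to time of death".

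Section 16.2 contains no censoring rule, so the sentence in 16.7 is the only one in the protocol. On presentation, section 16.5 says: "Time to event endpoints will be presented using Kaplan-Meier plots".

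On follow-up, section 10 says: "After progressive disease, patients will be followed by telephone for overall survival". In the study procedures table, the three-monthly column after progression is marked for overall survival and nothing else. Before progression, section 13.5 schedules disease markers every two months.

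**The concern.** What the sentence censors is an event whose registration is incomplete. It does not say that it censors patients without an event. A death reported by telephone with only the month known, or a next treatment whose start date is only roughly known, fits that description. Because imputation is barred, no date can be supplied, and the only route left is censoring at last contact.

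Censoring of that kind is informative by construction: the patient leaves the risk set because the event happened. The error always goes in the favourable direction. There is no control arm in which the same error would occur, and section 16.5 allows estimates to be compared with historical ones. The sentence also leaves open whether the last contact may be the very call that reported the event.

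**Working it through.** **1. What the wording permits.** Two readings are possible.

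| Reading | Patient with no known event | Patient with a known event, incomplete date |
|---|---|---|
| A. Ordinary right censoring | censored at last contact | not addressed; imputing a date is barred |
| B. Literal | not addressed | censored at last contact |

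Two things give B some weight. A patient without an event has no event registration that could be incomplete. And section 14.1 uses registered of adverse events in the sense of recorded. Even under A, the ban on imputation leaves a known event with a partial date without a permitted treatment other than censoring or omission.

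**2. Where incomplete dates could arise.** TTNT needs the start date of the next treatment, yet the post-progression column of the procedures table has no item for it. Deaths after progression are learned by telephone at three-monthly contacts. Progression is less exposed, since it rests on scheduled samples: "Serum free light chains (S-FLC) at study entry, start of every cycle and at every two months until progression".

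**3. The plan's own figure.** The protocol states no event rate, median or rate of incomplete dates, so there is nothing on this point to reproduce. Its only design calculation is the table of 95% Wilson intervals for n = 50 in section 16.1. All nine rows reproduce. For a proportion of 0.8:

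- centre = (0.8 + 1.96²/100) / (1 + 1.96²/50) = 0.8384 / 1.0768 = 0.7786
- half-width = 1.96 × √(0.16/50 + 1.96²/10000) / 1.0768 = 0.1090
- interval = 0.670 to 0.888, as printed, about 22 percentage points wide

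This serves below only as a yardstick.

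**4. Illustration for OS under reading B (assumed inputs).** Assume 50 treated patients, 12 deaths spread evenly over 36 months, and everyone else followed throughout. True 36-month survival is 1 − 12/50 = 76.0%. Suppose k deaths are instead censored up to three months earlier. A patient censored on average halfway through counts for about half a patient at risk, so survival is roughly 1 − (12 − k)/(50 − k/2).

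| k | Approximation | Simulated Kaplan-Meier mean (4000 data sets) |
|---|---|---|
| 0 | 1 − 12/50 = 76.0% | 76.0% |
| 1 | 1 − 11/49.5 = 77.8% | 77.7% |
| 2 | 1 − 10/49 = 79.6% | 79.5% |
| 3 | 1 − 9/48.5 = 81.4% | 81.4% |

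One death in 12 is 8% of deaths; three are 25%.

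**5. Illustration for medians (assumed inputs).** With exponential times, if a fraction f of events is recoded as censored, the hazard that Kaplan-Meier sees is about (1 − f) times the true one, so the median becomes about m/(1 − f). The simulation used 400,000 times, with the recoded events censored at the preceding scheduled contact (two-month grid for PFS, three-month grid for OS).

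| f | PFS, assumed m = 36 months: formula / simulated | OS, assumed m = 96 months: formula / simulated |
|---|---|---|
| 2% | 36.7 / 36.6 | 98.0 / 97.8 |
| 5% | 37.9 / 37.9 | 101.1 / 100.7 |
| 10% | 40.0 / 39.9 | 106.7 / 106.4 |
| 20% | 45.0 / 44.8 | 120.0 / 119.1 |

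The relative rise is therefore about 2%, 5%, 11% and 24% or slightly more. At f = 0 it is nil.

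**The case against.** The strongest reply is that the sentence is simply a clumsy statement of right censoring: an event time not fully observed is an incomplete one, and follow-up then ends at last contact. Under that meaning the rule adds no bias beyond the usual assumption of non-informative censoring. This stands as a possible reading. A reader might infer from the literal wording that the plan sets out to treat patients known to have died, progressed or been re-treated as event-free, and that its survival results are inflated. The protocol does not support that. It never mentions such patients in this rule, and nothing in it shows that undated events will occur.

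The protocol also makes them less likely. Assessments are scheduled, monitors check under section 14 that relapse data are documented and case report forms complete, and section 16.4 delays the main analysis until data are verified. The illustrations rest wholly on assumed inputs, and the shift for a single death (1.7 points) is small beside the yardstick interval of about 22 points. No test or decision depends on these curves.

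A further reply is that partial-date conventions belong in a statistical analysis plan, which is not shown. That would dispose of the point if the protocol were silent. It is not silent: it bars imputation, so a date convention in a later plan would contradict it. For that reason the correction belongs in 16.7.

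**Conclusion.** The point holds as a defect of wording, with low severity. As written, section 16.7 permits a known but incompletely dated event to be censored, and where that happens the OS, PFS and TTNT estimates are biased upward. The direction is certain under that use of the rule. The size is unknown, because it depends on a rate of incomplete dates that the protocol does not give. It is zero if all events are fully dated, and about 2% to 11% on the median if 2% to 10% of events are affected under the exponential assumption. TTNT and post-progression deaths look the most exposed, PFS the least. It does not follow that the trial's survival results are inflated; that would need both the literal reading and actual incomplete dates. The primary endpoint is binary, falls under worst-case imputation, and is not touched.

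**What to change.** Replace the time-to-event sentence in section 16.7 with wording such as:

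> Only patients with no known event are censored, at the last contact at which they were known to be event-free. An event known to have occurred is always counted as an event. If its date is incomplete, the date is set to the mid-point between the last contact known event-free and the contact that reported the event.

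The earliest and latest possible dates can serve as a sensitivity analysis. The mid-point is one workable convention; what matters is that it is fixed before the data are analysed. With contacts kept to schedule, it can misplace a date by at most half the interval: 1 month on the two-monthly schedule and 1.5 months on the three-monthly one.

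The cost is a few sentences in one section and a few lines of programming. The only downside is that the survival figures may become slightly less favourable.

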12.2.1 Dose modification guidelines for carfilzomib

In a case of study-related adverse event, the clinical investigator must assess its possible relationship to carfilzomib, lenalidomide and dexamethasone.

Local investigators can decide to not follow this dose modifications if they feel it is not in the best medical interest of the patient.

| Carfilzomib dose reduction guidelines for toxicity and dose modification | | | |
|---|--------------------------------|--------------------------------|--------------------------------|
| | 1 st dose reduction | 2 nd dose reduction | 3 rd dose reduction |
| 36 mg/m ² | 27 mg/m ² | 20 mg/m ² | 15 mg/m ² |

If a patient requires an interruption of carfilzomib of more than four weeks this study patient will be removed from study; all exceptions to this must be discussed with principal investigator. If the carfilzomib dose is reduced once, it will be continued for at least one cycle. In case this cycle is tolerated, the dose level prior to reduction may be resumed by the investigator's discretion. If carfilzomib is stopped permanently due to toxicity, all study medication will be stopped and the patient will proceed to end-of-study visit.

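### One last-contact censoring rule for all time-to-event endpoints suits OS but biases PFS upward for treated patients who leave without progression and are later contacted for survival

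*Protocol*

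**What the plan says.** Protocol 16.7 (Missing data) covers all time-to-event endpoints together. It rules out imputation for them and adds that "incomplete registrations of event will be censored at last time of contact". Section 16.2 defines the endpoint as "Progression-free survival (PFS) as defined as time from treatment initiation to progression defined using IMWG criteria for progressive disease" and gives it no censoring date of its own, so 16.7 governs. Section 16.5 presents time-to-event endpoints as Kaplan-Meier plots.

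Disease assessment is described in 13.5: "Serum protein electrophoresis and immunofixation (IFE) at study entry, start of every cycle and every two months until progression". Urine electrophoresis and free light chains follow the same timetable. In the study procedures table, evaluation of clonal disease is ticked at the two-monthly visits and at the end-of-treatment visit at progression.

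Patients can leave before progression. Section 9 allows withdrawal for, among other reasons, an adverse event, non-compliance or a change of therapy that the physician thinks better, followed by exit procedures and standard of care. Under 12.2.1, when carfilzomib is stopped permanently for toxicity, "all study medication will be stopped and the patient will proceed to end-of-study visit". The same section removes patients whose carfilzomib is interrupted for more than four weeks, unless an exception is discussed.

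On later contact, section 10 says: "There will be a post-study follow-up for overall survival in all patients, both with initial PET-CT positivity and negativity". The synopsis, under Duration of Study, has patients followed until death or loss to follow-up.

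**The concern.** A contact can show that a patient is alive. It does not by itself show that the patient is free of progression, which under the protocol's definition needs IMWG criteria and hence M-protein or light-chain measurements. When the last contact is later than the last assessment, the rule in 16.7 keeps the patient in the PFS risk set over a period in which a progression could not have been recorded. The denominator is too large for the events counted, and the curve sits too high.

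The error has one direction: it flatters KRd. It matters most if the single-arm PFS is set beside outside figures, and 16.5 leaves room for comparison with historical estimates.

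**Working it through.** **1. The protocol's own figure.** It states no PFS figure. Its only design figure is the precision table in 16.1. The Wilson interval for n = 50 and p = 0.5, with z = 1.96, has centre (0.5 + 3.84/100)/(1 + 3.84/50) = 0.500. Its half-width is 1.96 × √(0.25/50 + 3.84/10,000)/(1 + 3.84/50) = 0.134. That gives 0.366 to 0.634, as printed. The other eight rows also reproduce. This serves below only as a yardstick of imprecision.

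**2. Can last contact and last assessment separate?** For a patient who stays on study, hardly: contact and assessment share the two-monthly visit until progression. For a patient who leaves without progression, sections 9 and 12.2.1 provide an exit visit and state no further study assessment, while section 10 and the synopsis have survival contact going on. For that patient the two dates can be far apart.

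**3. Inputs that are assumptions.** None of these is in the protocol: exponential PFS with median 24 months; a fraction f of patients assigned to leave at a random time, either in months 0-4 or in months 1-6; leaving unrelated to prognosis; no progression recorded after leaving; survival contact maintained.

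**4. Hand calculation of 24-month PFS.** Let q be the probability that a patient assigned to leave has no progression before leaving. Averaging 2^(−u/24) over the leaving time u:
- months 1-6: q = (0.9715 − 0.8409)/(0.6931 × 5/24) = 0.905
- months 0-4: q = (1 − 0.8909)/(0.6931 × 4/24) = 0.944

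Under the last-contact rule these patients never have an event afterwards. Ignoring deaths and administrative censoring before month 24, the estimate is (1 − f) × 0.50 + f × q.

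At f = 20%: 0.8 × 0.50 + 0.2 × 0.905 = 0.581, or 0.589 with q = 0.944.

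For the median, solve 2^(−t/24) = (0.50 − f × q)/(1 − f). At f = 20% and q = 0.905 the right side is 0.319/0.8 = 0.399, so t = 24 × log2(1/0.399) = 31.8 months.

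**5. Simulation.** Two Kaplan-Meier simulations were run with 200,000 patients per scenario. The first had leaving in months 1-6, follow-up of 24-48 months and no deaths; it did not include 5%. The second had leaving in months 0-4, 24 months' uniform accrual, 12, 24 or 36 months' further follow-up, and median survival of 36 months after progression. The true values are 50% and 24 months.

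| Assigned to leave | Of 50 patients | 24-month PFS by hand (months 1-6 / 0-4) | 24-month PFS simulated | Median simulated (months) |
|---|---|---|---|---|
| 5% | 2.5 | 52.0% / 52.2% | 52.0-52.3% | 25.4-25.6 |
| 10% | 5 | 54.1% / 54.4% | 53.9-54.3% | 27.3-27.5 |
| 20% | 10 | 58.1% / 58.9% | 58.0-58.6% | 31.8-32.2 |
| 30% | 15 | 62.1% / 63.3% | 62.1-63.0% | 38.6-39.0* |

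*Not reached with 12 months' follow-up after the last entry.

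**6. Other true medians (second simulation).** With a median of 36 months, 24-month PFS reads about 65%, 66%, 70% and 73% against 63%. With 48 months it reads about 72%, 73%, 76% and 78-79% against 71%.

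**7. Unassessed time.** The median time credited to a patient who left was about 21, 32 and 42-44 months with 12, 24 and 36 months' follow-up after the last entry.

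**8. Alternative rule.** Censoring at the last assessment returned the true 24-month value, to within simulation error, in every scenario. That follows partly from the assumption that leaving is unrelated to prognosis.

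**The case against.** The strongest reply is that the protocol never schedules survival-only contact for a treated patient who has not progressed. The only such column in the study procedures table is the three-monthly one after progression. Section 10 places telephone survival follow-up after progression, the synopsis has the study run until all patients progress, and 13.5 continues assessments until progression without requiring that the patient be on treatment. If contact ends at the exit visit, the two dates nearly coincide. This stands as a limit. A reader might infer that section 10 puts every withdrawn patient on survival-only follow-up; it does not say so. Later contact is implied by its wording, "There will be a post-study follow-up for overall survival in all patients", and by the synopsis. That is enough for the rule to go wrong, but not enough to say how often.

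Second, the exit rate is unknown. The carfilzomib exits arise within four 28-day cycles, and patients not expected to tolerate full-dose KRd are excluded. At 5% the shift at 24 months is 1-2 points, small beside the ±13 points of the 16.1 table at 0.5. This stands: the 32- and 39-month medians need 20-30% leaving and should not be read as predictions.

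Third, a call may turn up a progression, as the telephone/fax PFS follow-up of PET-negative patients assumes. That would shrink the bias, but nothing requires it for treated patients who have left.

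Fourth, a reader might infer that carrying patients through a new myeloma treatment started before progression is itself an error. It is not. Following for progression regardless of later treatment is a legitimate choice, and new treatment is captured by TTNT.

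Finally, censoring dates are often left to the SAP. Here the protocol has already fixed one, and an SAP would have to depart from it.

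**Conclusion.** The point holds in a limited form. As written, 16.7 applies to PFS a censoring date that suits only OS, and for treated patients who leave without progression and are contacted later, the resulting bias is upward. Its direction follows from the rule; its size does not, because the protocol gives no exit rate. Under the stated assumptions and a true median of 24 months, 24-month PFS is overstated by about 2 points if 5% leave, 4 if 10%, 8-9 if 20% and 12-13 if 30%; with longer true medians the shift is smaller. A reader might infer that reported PFS will be heavily inflated. The documents do not support that: patients who stay on study are little affected, and few exits would mean little bias. PET-negative patients are not at issue, since PFS runs from treatment start and they receive no study treatment. PFS is secondary, with no hypothesis or sample size resting on it, and the primary endpoint is untouched. The rule should be corrected because it is wrong for this endpoint and cheap to change.

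**What to change.** In 16.7, separate the endpoints. Keep last contact as the censoring date for OS. For PFS, censor patients without recorded progression at the date of their last adequate IMWG disease assessment showing none, and say what makes an assessment adequate.

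State in advance how a new myeloma treatment before progression is handled: follow through it, censor at the last assessment before it, or count it as an event. Any of these can be defended if chosen beforehand.

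The cost is small. Assessment dates are already collected under 13.5 and the procedures table, and the start of next treatment is collected for TTNT; no visit or sample-size change is needed. There will be fewer patients at risk late in the curve, and estimated PFS will be somewhat shorter. The new rule is not a full remedy: if patients who leave differ in prognosis from those who stay, censoring at the last assessment can also be biased, so the number leaving without progression and their reasons should be reported beside the curve.
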